6.5 Interim Analysis

Interim analyses of efficacy of 7% HS will be performed.

7. STUDY INTERVENTION (drug, device or other intervention details)

- **Description:** Sodium chloride 7% solution, which is commercially available as Hypersal® (PARI Respiratory Equipment, Inc, Midlothian, VA).
- **Receipt/Storage:** HS will be delivered and stored within the CEMALB.
- **Packaging/Labeling:** This is an open label study.
- **Dosing:** 4mL vial of HS is nebulized and inhaled until the dose is complete, typically 15 minutes.
- **Treatment compliance and Adherence:** Subjects are observed during all dosing periods.
- **Drug Return/Destruction:** NA
- **Drug Accountability:** NA

8. STUDY INTERVENTION ADMINISTRATION (if applicable)

- **Randomization procedures:** N/A
- **Blinding procedures:** This is an open label study.

9. SAFETY MANAGEMENT

• Definition of Adverse Event (AE) and Serious Adverse Event (SAE)

- An adverse event for a given volunteer will be defined as failure of any of the safety criteria outlined above. Any decrease in lung function as outlined above will be considered an adverse event. Any symptoms that induce a volunteer to seek medical attention from any provider within 96 hours of a study visit will be considered an adverse event. A serious adverse event will be defined as any event that requires hospitalization or results in life threatening illness or injury, permanent (or likely to be permanent) illness or injury, or death if these events occur within 96 hours of a study visit (or if the clinical scenario leading up to hospitalization, illness, injury or death begins within 96 hours of a study treatment visit).

Grading criteria

- In addition to determining whether an adverse event fulfills criteria for a serious adverse event or not, the severity of adverse events experienced by study participants will be graded according to the criteria set forth in the National Cancer Institute's Common Terminology Criteria for Adverse Events Version 4.0. This document (referred to herein as the NCI-CTCAE manual) provides a common language to describe levels of severity, to analyze and interpret data, and to articulate the clinical significance of all adverse events.
- All adverse events whether or not listed in the NCI-CTCAE will be graded on a scale from 1 to 5 according to the following standards in the NCI-CTCAE manual (A semi-colon indicates 'or' within the description of the grade.):
- Grade 1 = Mild; asymptomatic or mild symptoms; clinical or diagnostic observations only; intervention not indicated.
- Grade 2 = Moderate; minimal, local or noninvasive intervention indicated; limiting age-appropriate instrumental ADL (preparing meals, shopping for groceries or clothes, using the telephone, managing money, etc).
- Grade 3 = Severe or medically significant but not immediately life-threatening; hospitalization or prolongation of hospitalization indicated; disabling; limiting self care ADL (bathing, dressing and undressing, feeding self, using the toilet, taking medications, and

not bedridden).

- Grade 4 = Life-threatening consequences; or urgent intervention indicated.
- Grade 5 = Death related to AE.
- **Adverse Event/Serious Adverse Event reporting procedures:** AE's and UP's will be reported to the IRB. The IRB, DSMB, and funding agency will be notified of any SAEs. The DSMB will review progress after the first 5 participants have completed the protocol or at 6 months after enrollment begins, whichever is soonest, and then every 6 months thereafter.
- **Medical Emergency procedures:** There is a study physician available for all inhalation procedures. A code cart and Automated External Defibrillator (AED) are available in the event of a cardiopulmonary event. Albuterol, both inhalers and nebulizers, are available in the event of bronchospasm. If a subject has an event that does not immediately respond to care in the research lab, he/she will be transported via EMS to UNC Healthcare for treatment.
- **Data Safety Monitoring Plan:** Data is initially recorded on paper documents, and the documents are maintained in a binder which is kept in a locked office within the EPA Human Studies facility. The EPA HSF is a secure facility with a guarded entrance and requires identification for entry. This data is then entered into REDCap by an initial data entry person, and confirmed by a second user.

- **Potential Risks:**

Potential Risks of Hypertonic Saline Inhalation:

Inhalation of hypertonic saline carries a small risk of bronchospasm, which may lead to the onset of asthma symptoms.

Potential Risks of Spirometry:

Potential risks include possible lightheadedness or wheezing.

Potential Risks of Mucociliary clearance scan:

The radiation risks for the MCC scan, including the Cobalt 57 transmission scan and the Americium 241 disks, which are used as fiducial markers is approximately 133 mRems. Adults in the New York City area receive about 300mRems per year in natural radiation exposure.

Potential Risks of Sputum Induction:

- Sputum induction may induce cough, chest tightness or bronchospasm **Protections Against Risk:**

Protections to Minimize Risk of Hypertonic Saline Inhalation:

A CEMALB physician is present in the building at all times during HS inhalation. All asthmatic subjects are pretreated with albuterol inhalation prior to hypertonic saline administration. Additional albuterol will be given after HS inhalation if FEV declines by $\geq 10\%$ from that day's baseline at the 30 minute spirometry measurement, if the participant develops symptoms of an asthma attack such as wheezing, or if the participant requests albuterol treatment.

Protections to Minimize Risk of Spirometry:

Subjects will be seated in a non-rolling chair when spirometry is performed and standard methodology conforming to the American Thoracic Society guidelines for measurement of spirometry will be used. Subjects will be instructed to notify the study staff if they feel lightheaded, and albuterol will be available in the event the subject experiences any unanticipated bronchoconstriction.

Protections to Minimize Risk of Mucociliary clearance scan:

Radiation history is collected. Any subject who will exceed safe annual exposure limits will not be enrolled.

Protections to minimize Risk of Sputum Induction:

Subjects will have been given 4 puffs of albuterol in the 2-3 hour time period prior to sputum induction. In the event of bronchospasm associated with the induction, albuterol will be

immediately available for rescue.

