temperature, respiratory rate (RR), heart rate (HR), oxygen saturation, blood pressure (BP), and symptom questionnaires will be collected. Fractional exhaled Nitric Oxide (FeNO) will be measured in exhaled breath (used to classify asthma as being predominated by eosinophilic vs non-eosinophilic airway inflammation). Spirometry will be performed to establish that day's baseline values. FEV1 must be $\geq 70\%$ before albuterol. Participants will inhale Tc99m-SC and immediately be scanned by gamma scintigraphy to measure deposition of the radiolabeled particles in the airways (4 minute scan). MCC will be assessed over a 2-hour period to define baseline MCC. A baseline symptom questionnaire will be obtained. Subjects will then undergo a sputum induction procedure

Any subject who experiences a $\geq 10\%$ reduction in FEV1 from that day's baseline at the spirometry measure, or who increases HR, BP or RR more than 30% from baseline, or with audible wheezing on physical exam, or participants who report any symptom as severe (score of 3) on the symptom questionnaire will be considered intolerant to HS and will not be included in further study. Oxygen saturation will be monitored, and a transient decrease is an expected finding when using mucolytic agents. Sustained ($< 90\%$ for more than 1 hour) decrease in oxygen saturation will be considered intolerance. Testing will be stopped at any point the volunteer requests that it stop. Any subject who does not tolerate HS will be monitored until the vital signs return to normal limits, and the symptoms resolve. Subjects will be discharged to home with contact information for a study physician, an asthma action plan reviewed by the study coordinator, and emergency medications if needed overnight, including an albuterol MDI with spacer and 60 mg of prednisone. Subjects will be instructed to call the physician on call if they require prednisone treatment.

4.2 Visit 2 Follow-up Baseline Visit: Participants will return the following morning for vital signs, symptom questionnaire, 24-hour lung retention imaging, FeNO, and spirometry. Subjects who tolerate the HS dose and do not meet stopping criteria will be invited back for the remaining study visits.

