5.2 Pharmacokinetic Evaluation (if applicable)

None

5.3 Safety Evaluations: The primary safety criteria will be change in FEV1 from baseline measures obtained on the same day. A drop in FEV1 by 10% at the 30-minute mark after HS inhalation will be considered an adverse event for patient safety and will result in withdrawal of the subject from further participation in the study.

During visit 1, subjects will be monitored for 1 hour after HS inhalation. If a subject's FEV1 is reduced by $\geq 10\%$ from that day's baseline at the 5-minute mark, spirometry will be repeated every 5 minutes up to 30 minutes. If at the 30-minute mark FEV1 is still reduced by $\geq 10\%$, 4 puffs of albuterol will be administered. Albuterol 4 puffs with spacer will be repeated if the participant has symptoms, or if FEV1 does not spontaneously return to within 5% of baseline values at the 1-hour mark.

Oxygen saturation will be monitored during the HS inhalation through the rest of the day's study procedures. Several studies have shown that the oxygen saturation drops transiently in patients with CF and COPD when they inhale a mucolytic agent. It is anticipated that asthmatic subjects will have a similar response.

Vital signs are monitored, including HR, RR, and BP. Auscultation is performed to determine if wheezing is present.

We will assess symptoms at baseline, prior to HS, and following HS whenever vital signs are measured. We will use the following symptom score questionnaire:

Symptom score (scale 0-none, 1-mild, 2-moderate, 3-severe):

Malaise____, Fatigue____, Shortness of Breath____, Cough____, Myalgia____,
Chills____, Fever____, Headache_____

Mild: Symptom minimally noticeable but would not ordinarily cause you to stop normal activities such as going to work or school and would not keep you from undertaking physical exercise.

Moderate: Symptom present but would not ordinarily cause you to stop normal activities such as going to work or school, although it might stop you from doing physical exercise ("working out")

Severe: Symptom clearly present and would cause you to consider not going to work or school or seek medical attention (such as calling a health care provider, going to student health, going to the emergency room, or taking medications for these symptoms).

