6.2 Secondary Endpoints

a. change in MCC from baseline immediately after albuterol inhalation. This endpoint is of exploratory interest.

b. Safety measures for HS treatment in moderate to severe asthmatics will include change in the following from baseline:

- Vital signs (HR, RR, BP and oxygen saturation)
- Spirometry (FEV1, FVC)
- Symptom Questionnaires
- Physical exam (wheezing on chest auscultation, for example)

We will also assess:

- Adverse events and Serious Adverse events
- Proportion of participants who are deemed 'intolerant' to HS (i.e. those who experience a persistent reduction in FEV1 of $\geq 10\%$ from that day's baseline at 30 minutes post-HS, those who report shortness of breath, those who report a score of "3" for any individual symptom criterion, or those who experience oxygen saturation levels below 90% for > 1 hour).

Safety endpoints will be assessed continuously during the study period for monitoring of adverse events and individual stopping criteria. All adverse events whether or not listed in the NCI-CTCAE (see Section 9) or whether they are or are not related to study participation will be graded on a scale from 1 to 5 according to the standards in the NCI-CTCAE manual. Adverse events will be reported to the UNC IRB, the UNC DSMB, and the NHLBI project officer. The DSMB will review the protocol after 5 subjects have completed study procedures or at 6 months after enrollment begins, whichever is soonest, and then every 6 months thereafter.

Exploratory endpoints will also be assessed. These will focus on sputum cellularity, mediators in sputum (e.g. T1 cytokines: IL-1 β , IL-6, IL-8, TNF α , T2 cytokines, IL-4, IL-5, IL-13), eicosanoids,

and mucins (total mucins, MUC5AC, MUC5B).

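### Section 9 has no general adverse-event clause, so mild or moderate symptoms other than shortness of breath, and wheeze or chest tightness that clears after the supplied inhaler, can go uncounted

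*Combined protocol and SAP*

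**What the plan says.** Section 9 (Safety Management) gives three routes to an adverse event:

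- **Criterion failure:** "An adverse event for a given volunteer will be defined as failure of any of the safety criteria outlined above".
- **Lung function:** "Any decrease in lung function as outlined above will be considered an adverse event". Section 5.3 supplies the threshold: "A drop in FEV1 by 10% at the 30-minute mark after HS inhalation will be considered an adverse event".
- **Care-seeking:** "Any symptoms that induce a volunteer to seek medical attention from any provider", if this happens no more than 96 hours from a visit.

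No clause covers any other untoward sign or symptom.

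The grading scale in the same section starts at "Grade 1 = Mild; asymptomatic or mild symptoms; clinical or diagnostic observations only; intervention not indicated". Section 6.2 says that "All adverse events whether or not listed in the NCI-CTCAE (see Section 9) or whether they are or are not related to study participation will" receive a grade from 1 to 5, and that adverse events go to the IRB, the DSMB and the NHLBI project officer.

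On discharge, Section 4.1 provides "emergency medications if needed overnight, including an albuterol MDI with spacer and 60 mg of prednisone", and Section 4.9 confirms that every subject receives the inhaler. The instruction in Section 4.1 to telephone the physician on call is tied to needing prednisone. No equivalent is stated for using albuterol.

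**The concern.** The definition and the scale it feeds do not match. Grade 1 covers mild symptoms that need no intervention, but a symptom of that kind rarely sends anyone to a provider, and most such symptoms fail no safety criterion. The definition also sits awkwardly with the discharge arrangements, which equip the subject to treat overnight airway symptoms at home.

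Safety of HS is a stated secondary objective, adverse events are a listed safety assessment, and Section 9 names bronchospasm as the risk of inhaling HS. If the counting rule omits mild symptoms and short-lived airway symptoms, the adverse-event table gives its readers a picture that is thin at the low grades. With 28 subjects recruited, a few uncounted events would be visible in that table.

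**Working it through.** There is no stated figure to reproduce. The check is to follow each kind of symptom through the criteria that Section 9 points to.

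**Inputs**

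- Section 5.3: eight questionnaire items (malaise, fatigue, shortness of breath, cough, myalgia, chills, fever, headache), each scored 0 to 3. Wheeze and chest tightness are not items.
- Section 4.11, criteria after HS: a 10% or greater FEV1 fall at 30 minutes; exacerbation symptoms such as wheeze, but only if they continue; a vital-sign rise above 30%; low oxygen saturation for more than an hour; shortness of breath of any degree, joined by an 'and' to any symptom scored 3; need for oral corticosteroid.
- Section 6.2: shortness of breath and a score of 3 are listed as separate grounds for intolerance.
- Section 5.3, after HS: a moderate score leads to assessment by a study physician. Only a severe score leads to exclusion.

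**Step 1: questionnaire symptoms scored mild or moderate after HS**

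- Item levels at score 1 or 2: 8 × 2 = 16.
- Levels that fail a criterion, reading shortness of breath as Section 6.2 does: 1 × 2 = 2.
- Levels outside the definition unless care is sought: 16 − 2 = 14.
- Highest total score with no shortness of breath and nothing severe: 7 × 2 = 14, out of a maximum of 8 × 3 = 24.

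If the 'and' in Section 4.11 required both conditions, shortness of breath scored 1 or 2 with nothing severe would fail no criterion there, and all 16 levels would fall outside. Section 6.2 reads against this, so 14 of 16 is the better-supported count.

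A moderate cough shows the gap. Section 5.3 requires a physician to assess it, yet nothing makes it an adverse event: the protocol, not the volunteer, initiates that assessment.

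**Step 2: overnight wheeze or chest tightness without shortness of breath, relieved by the supplied inhaler**

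| Route | Result |
|---|---|
| Criterion: exacerbation symptoms | Not met, because they did not continue |
| Criterion: symptom score | Neither symptom is a questionnaire item |
| Lung function | The stated threshold applies 30 minutes after HS, not overnight |
| Care from a provider | None sought; the call instruction covers prednisone only |

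Section 3.1 has staff ask about overnight symptoms the next morning, but no rule turns the answer into an adverse event. The appendix table marks a physical examination at Visits 1, 3 and 5, not at the next-morning visits.

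**Step 3: comparison with the grading scale**

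Grade 1 can still be populated by asymptomatic findings, such as an FEV1 fall that meets the threshold, and by mild shortness of breath. What is largely missing is the rest of the mild symptoms that its wording covers.

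**The case against.** The strongest reply is that the criteria reach further than they first appear to.

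- Shortness of breath, the questionnaire symptom closest to bronchospasm, appears to count at any severity.
- Continued wheeze counts under Section 4.11, and Section 4.1 treats audible wheeze on examination as intolerance without requiring that it continue.
- The Section 5.3 description of a severe symptom includes medication use among its examples of seeking medical attention. A listed symptom treated with the inhaler could therefore score 3 and fail a criterion.
- The data are not lost. Questionnaires and auscultation are separate safety measures in Section 6.2, adverse-event review is scheduled at every visit, and Section 4.9 collects concomitant medication and returned prednisone.

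Most of this stands, and it rules out three stronger readings. A reader might infer that all mild or moderate symptoms drop out, but shortness of breath does not. A reader might infer that any self-treated bronchospasm escapes, but an episode with shortness of breath, or with a listed symptom rated severe because medication was taken, is caught when reported. A reader might infer that the trial as a whole will understate the harm of HS, but the other safety measures and the intolerance proportion remain.

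The reply does not close the gap. The severity description applies only to listed symptoms, which exclude wheeze and tightness. It also conflicts with the Section 9 requirement that care come from a provider. Symptoms are scored when vital signs are taken, with no stated recall period, so an episode that resolved overnight may score 0. Adverse-event review at each visit applies whatever definition Section 9 gives.

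**Conclusion.** The point holds in a limited form. Followed as written, Section 9 leaves out mild or moderate cough, malaise, fatigue, myalgia, chills, fever and headache after HS unless care is sought. It can also leave out wheeze or chest tightness without shortness of breath that resolves after the supplied inhaler. The graded and reported adverse-event table will under-represent low-grade symptom events, contrary to its own Grade 1 wording.

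The size is 14 of 16 mild-or-moderate item levels. That counts what the rule excludes and is not a prediction of how many events will be missed, since the documents give no symptom frequencies. It assumes that shortness of breath stands alone as a criterion, as Section 6.2 has it, and that the safety criteria meant are those that apply after HS. Section 9 does not say so: if it also means the pre-inhalation criteria in Section 4.11, a moderate symptom before HS would literally be an adverse event while the same symptom afterwards would not.

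This is a stated rule that undercounts a listed safety endpoint, not a missing detail, and it should be corrected.

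**What to change.** Replace the Section 9 definition with wording such as: *any new or worsened sign or symptom after the first study procedure, whether or not care was sought and whether or not it is thought related, including symptoms for which the supplied albuterol or prednisone was used after discharge.* Then:

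- Keep failures of the safety criteria as a separately flagged subset of adverse events.
- At Visits 2, 4, 6 and 7, ask about and record inhaler and prednisone use since discharge. This overlaps partly with the concomitant-medication record but ties the use to a symptom.
- Grade all resulting events 1 to 5, as Section 6.2 already commits to do.
- Reconcile Sections 4.1, 4.11, 5.3, 6.2 and 9 on three matters: whether shortness of breath alone is a criterion, which wheeze counts, and whether taking medication is seeking medical attention. State also which list of criteria Section 9 refers to.

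The cost is one revised definition, one added question at visits that already include adverse-event review, and more low-grade events to list and report. The new definition and the added question change no dose, treatment or stopping rule; how the criteria themselves are reconciled is for the investigators.

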4.9 Concomitant Medication documentation: Concomitant medications are collected at the screening visit and throughout the study visits. Subjects will use previously prescribed medication for their asthma. Subjects will not be asked to withhold any LABA/steroid combination medication on the morning of study visits. The study will provide all subjects with an albuterol MDI with spacer, and with 60 mg of prednisone as part of the asthma action plan at discharge. Subjects will be allowed to keep albuterol MDI with spacers for their personal use. Subjects will be asked to return unused prednisone tablets to the study staff during the follow-up visits.

4.10 Rescue medication administration: As with any testing in a population of subjects with asthma, albuterol (Ventolin® HFA) will always be available for rescue. There is also a code cart immediately available with epinephrine autoinjectors. Oxygen is available for supplementation if required.

4.11 Subject Completion/ Withdrawal procedures: Subjects are considered completed when the final 24-hour imaging, symptom questionnaire, vital signs and spirometry are collected. Subjects may withdraw at any time. Subjects will be asked to return to the lab for a final visit if they withdraw from the study prior to completion of all study procedures to monitor safety.

Subjects may be withdrawn at any time for safety concerns. Subjects who have any unanticipated problems (UPs) with the study procedures will be monitored until resolution of the symptoms.

Criteria for safety prior to HS inhalation:

(Subjects not meeting these criteria will not proceed with HS inhalation):

1. FEV₁ of at least 70% of predicted
2. FEV₁ within 10% of baseline value established at the screening visit.
2. Baseline oxygen saturation of at least 93%.
3. No history of viral respiratory tract symptoms within 4 weeks of challenge.
4. Vital signs within the previously defined normal parameters.
5. Symptom questionnaire score ≤ 2, , and no more than mild symptoms (ranked as “1”) reported for any category (see Section 5.3).

Criteria for safety of a given individual following HS inhalation which would suspend the individual from further participation in the study will include:

1. A 10% or greater decline in FEV₁ (from that day's baseline) at the 30-minute spirometry assessment.
2. *Continued* Symptoms of asthma exacerbation such as wheezing or respiratory distress.

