3. Heart rate, blood pressure, or respiratory rate increase of more than 30% from baseline values (established on the same day).
4. Oxygen saturation < 90% for > 1 hour.
5. ANY reported shortness of breath, and any symptom ranked as severe (“3”).
6. Requirement of oral corticosteroid treatment for exacerbation of asthma associated with the HS inhalation.

Safety criteria for initiating suspension of further study until consultation with the DSMB and IRB will include the following:

1. The occurrence of any Serious Adverse Event.
2. If 3 of the first 10 participants fail the individual safety criteria outlined above.

Subjects will be under direct supervision of a study physician throughout the HS inhalation and MCC measurement, and will have contact information for after-hours access to a study physician. An asthma action plan with emergency medications will be provided to each subject after the HS visits in the event of an unexpected event, such as wheezing or bronchospasm overnight.

4.12 Screen failure procedures. For subjects who do not meet enrollment criteria, all study related activity will stop once it is determined that the subject does not meet criteria.

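### The hypertonic saline intolerance proportion is tied to a visit at which 7% saline is not given, and sections 4.1, 4.11 and 6.2 define intolerance differently

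*Combined protocol and SAP*

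**What the plan says.** Section 2.2 says HS safety will be evaluated through the proportion intolerant to HS and refers to section 5.3. Section 5.3 sets FEV1 and symptom rules but never defines the term.

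Two other sections do.
- **Section 6.2** gives a closed list. It opens with "those who experience a persistent reduction in FEV1 of" 10% or more at 30 minutes after HS, then adds any reported shortness of breath, any symptom scored 3, and saturation under 90% lasting over an hour.
- **Section 4.1** (Visit 1) counts an FEV1 fall, a symptom scored 3 and sustained desaturation. It also counts a participant "or who increases HR, BP or RR more than 30% from baseline, or with audible wheezing on physical exam".

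Section 4.11 lists the findings after HS that suspend an individual. Three are absent from 6.2:
- continued "Symptoms of asthma exacerbation such as wheezing or respiratory distress" (item 2);
- "Heart rate, blood pressure, or respiratory rate increase of more than 30% from baseline values (established on the same day") (item 3);
- "Requirement of oral corticosteroid treatment for exacerbation of asthma associated with the HS inhalation" (item 6).

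Section 4.11 also pauses the study "If 3 of the first 10 participants fail the individual safety criteria outlined above".

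Section 9 allows additional albuterol after HS for a 30-minute FEV1 fall, and also "if the participant develops symptoms of an asthma attack such as wheezing, or if the participant requests albuterol treatment".

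Section 6.3 reports the proportion, with a 95% confidence interval, among enrolled patients who do not tolerate HS at baseline. In the Appendix table, nebulized HS is marked only at Visit 5.

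**The concern.** There are three separate problems with one reported number.

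**Visit and denominator.** Taken literally, 6.3 counts reactions at Visit 1, where the only saline is the 3%, 4% and 5% sputum induction described in section 5. Reactions to the 7% dose would then not be counted. If the numerator is moved to Visit 5 but the denominator stays at everyone enrolled, people who never inhaled 7% HS dilute the proportion. Those excluded as intolerant at Visit 1 under 4.1 are among them.

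**Definition.** A participant suspended under 4.11 for continued wheeze, a vital-sign rise or oral corticosteroid need can be tolerant under 6.2. A participant with mild breathlessness is intolerant under 6.2 but not under 4.1.

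**Early rescue.** Albuterol given before the 30-minute spirometry can reverse the fall that 6.2 is meant to detect. A fall reversed by a bronchodilator has not been shown to be transient, and 6.2 does not say how to classify it.

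At stake is the summary that 2.2 promises on whether these patients tolerate 7% HS.

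**Working it through.** **Denominators.** The plan states no expected value for the proportion, so there is none to reproduce. Sections 3.3 and 6.4 give 28 recruited, and 6.4 gives 21 before inflation: 21 × 1.30 = 27.3, rounded up to 28. One participant is 1/28 = 3.6 points or 1/21 = 4.8 points.

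**The lists side by side.**

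| Finding | 6.2 | 4.1 | 4.11 |
|---|---|---|---|
| FEV1 down 10% or more | yes, at 30 min | yes, no time given | yes, at 30 min |
| Shortness of breath below score 3 | yes | no | yes, if item 5 means 'or' |
| Any symptom scored 3 | yes | yes | yes, if item 5 means 'or' |
| Saturation below 90% for over 1 h | yes | yes | yes |
| Wheeze | no | audible on exam | continued wheeze or distress |
| HR, BP or RR up more than 30% | no | yes | yes |
| Oral corticosteroid for HS-associated exacerbation | no | no | yes |

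Item 5 of 4.11 joins shortness of breath and a severe symptom with 'and', so both readings were checked.

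**Direction.** Seven yes/no findings give 2^7 = 128 patterns. These are logical possibilities, not frequencies.
- Against 4.1: 6 patterns are intolerant under 4.1 only, and 2 under 6.2 only. The 6 have wheeze and/or a vital-sign rise (3 combinations) and none of the 6.2 findings, with or without corticosteroid (× 2). The 2 have shortness of breath below score 3 and nothing else 4.1 counts, with or without corticosteroid.
- Against 4.11 with item 5 as 'or': 7 under 4.11 only (2^3 − 1), none under 6.2 only.
- Against 4.11 with item 5 as 'and': 7 under 4.11 only, 2 under 6.2 only.

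**Illustrative sizes.** Every numerator is assumed. Intervals are Clopper-Pearson: lower limit Beta(0.025; k, n−k+1), upper limit Beta(0.975; k+1, n−k).

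Take 28 participants, 2 of whom meet both 6.2 and 4.1:
- Two more with wheeze or a vital-sign rise only: 6.2 gives 2/28 = 7.1% (0.9 to 23.5), 4.1 gives 4/28 = 14.3% (4.0 to 32.7).
- Two more with shortness of breath below score 3 only: 6.2 gives 14.3%, 4.1 gives 7.1%.
- Two of each: both give 14.3%, while the two lists combined give 6/28 = 21.4% (8.3 to 41.0).

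With 0 to 4 participants of each kind, 6.2 minus 4.1 runs from −4/28 = −14.3 points to +4/28 = +14.3 points.

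Denominator: 4 intolerant of 21 dosed is 19.0% (5.4 to 41.9). The same 4 over 28 enrolled is 14.3%, lower by the factor 21/28 = 0.75.

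Extreme case against 4.11: if 3 of the first 10 failed only on items 2, 3 or 6, the study pause would trigger at 30% (6.7 to 65.2) while 6.2 read 0/10 (0 to 30.8).

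**Early rescue.** FEV1-triggered albuterol comes at 30 minutes, after the deciding measurement (sections 5.3 and 9). Only rescue for symptoms or on request can come earlier. Any shortness of breath already counts, and the score-3 anchor in 5.3 includes "or taking medications for these symptoms". What remains is rescue for wheeze or chest tightness (neither is a questionnaire item), or on request, without shortness of breath, a score of 3 or a 30-minute FEV1 fall.

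**The case against.** The best defence starts from 2.2, which points to 5.3. That section makes the 30-minute FEV1 fall the primary safety criterion, excludes for a score of 3, and sets no intolerance threshold for wheeze or vital signs. On those items 6.2 follows the section it is referred to. Section 4.1 describes a visit without 7% HS, and 4.11 contains suspension rules, which may reasonably be wider than an endpoint. A vital-sign rise may come from the 4 puffs of albuterol given before HS (section 4.5), and a rescue on request may involve no bronchospasm. Leaving these out of a composite is defensible.

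This stands in part: a narrower endpoint could be chosen deliberately. But 4.1 uses the same term with different contents, and nothing says the difference is intended. Nor does the defence explain reporting at baseline.

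It is also true that 6.2 reports wheeze, vital signs, spirometry and adverse events separately, that section 9 makes failure of any safety criterion an adverse event, and that the study pause runs on 4.11. The reactions are therefore not hidden. Separate tables still do not give the number of people intolerant, because components overlap.

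A reader might infer that the proportion can only be too low. The documents do not support that. Each omitted item, and unclassified early rescue, can only lower the count or leave it unchanged. But 6.2 counts shortness of breath at any grade, whereas 4.1 requires a score of 3 and 5.3 excludes only for one, so the 6.2 count can exceed a 4.1 count.

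**Conclusion.** The point holds as an inconsistency of definition, visit and denominator. The plan does not fix who is counted as intolerant, to which saline exposure, or out of how many. A participant suspended after 7% HS can be reported as tolerant.

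The net direction against 4.1 is open. One-way understatement holds only against 4.11 with item 5 read as 'or', or against a combined list. Early rescue is a minor part.

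The firm size is 3.6 to 4.8 points per reclassified participant, and it assumes 28 or 21 in the denominator. Anything larger rests on assumed counts, since the documents give no reaction or rescue rate. No hypothesis test uses the proportion, and the primary MCC comparison does not depend on it. The correction should be made because 2.2 names this number as its safety evaluation and the repair is cheap.

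**What to change.** 1. **Section 6.3.** Define the proportion as intolerance to the 7% HS dose at Visit 5, among participants who received that dose. Report Visit 1 sputum-induction exclusions separately.
2. **Sections 4.1, 4.11 and 6.2.** Use one definition: the present 6.2 list, keeping any shortness of breath, plus audible wheeze on examination, an HR, BP or RR rise above 30% from that day's baseline, and oral corticosteroid for an HS-associated exacerbation. Word item 5 of 4.11 with 'or', and bring the score-3 exclusion in 5.3 into line.
3. **Rescue.** Record the time and reason for each albuterol rescue, and flag FEV1 values taken after it. Report the proportion with and without counting rescue before the 30-minute FEV1.
4. **Reporting.** Give the count for each component.

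The cost is a few sentences and a time-and-reason field on the case report form. The rules for giving rescue do not change. Some vital-sign rises or request-only rescues will be counted that are not HS reactions; the component counts and the two versions of the proportion make this visible. Counting any shortness of breath in 4.1 could exclude a few more people at Visit 1, which would draw on the 30% attrition allowance.
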